#### **4.1.4 Maintenance Phase, Double-blind, Parallel Groups (24 months)/104 weeks)**

As soon as possible after the participant is confirmed to be normokalaemic at the end of the run-in phase (based on local laboratory S-K results from Visit 6a), the participant will enter the maintenance phase. The date of randomisation is Day 1 of the maintenance phase (Visit 6b).

Participants will be randomised in a 1:1 ratio to receive either SZC or matching placebo. The starting dose of SZC/placebo will be the same dose as the last dose of SZC during the run-in phase. Lisinopril and valsartan will be continued at the same doses assigned at the end of the run-in phase. As described in the run-in phase, if there is a shortage of valsartan in a local market, valsartan can be temporarily substituted with irbesartan until the shortage of valsartan is resolved (see Section 4.1.3 and [Appendix E](#)).

Two safety visits will occur 2 and 7 ( $\pm 1$ ) days after randomisation and will include evaluation of S-K by local laboratory. The investigator must ensure that the choice of date for randomisation will allow for these 2 safety visits to occur 2 and 7 ( $\pm 1$ ) days after randomisation, respectively. Participants will then be monitored for approximately 24 months (through Week 104) for efficacy and safety assessments. A final safety follow-up visit will be conducted at Week 105, one week after the participant's last dose, after which the participant will exit the study.

See Section 6.6 for instructions on dose modification, including monitoring lisinopril/valsartan titration (Section 6.6.1) and management of abnormalities of S-K (Appendix C), use of SZC/placebo for management of S-K immediately after randomised withdrawal, ie, up to Week 6 of maintenance phase (Section 6.6.4), and additional unscheduled visits for titration of lisinopril/valsartan (Section 6.6.5).

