##### **Visit 7 (2 days after Visit 6b/randomisation)**

- If S-K  $\geq 3.5$  and  $\leq 5.0$  mmol/L, continue lisinopril/valsartan at the same dose; the participant must return 5 ( $\pm 1$ ) days later to Visit 8 for a local S-K laboratory measurement.
- If S-K is  $> 5.0$  and  $\leq 5.5$  mmol/L and SZC/placebo IS NOT at maximum of 15 g QD, increase SZC/placebo to 15 g QD AND reduce lisinopril/valsartan one step. If lisinopril/valsartan is at the lowest dose, pause dosing and assess re-initiation of these agents at starting doses (STEP 1) during the next visit. The participant must return 5 ( $\pm 1$ ) days later to Visit 8 for a local S-K laboratory measurement.
- If S-K is  $> 5.0$  and  $\leq 5.5$  mmol/L and SZC/placebo IS at maximum of 15 g QD, reduce lisinopril/valsartan one step. If lisinopril/valsartan is at the lowest dose (STEP 1), pause dosing and assess re-initiation of these agents at STEP 1 starting doses during the next visit. The participant must return 5 ( $\pm 1$ ) days later to Visit 8 for a local S-K laboratory measurement.
- If S-K is  $> 5.5$  mmol/L and:
  - Lisinopril/valsartan is at the lowest dose, permanently discontinue lisinopril/valsartan and consider short-term rescue therapy and management of hyperkalaemia as per SoC at the investigator's discretion and local practice. Follow up at Visit 8 for monitoring of local S-K laboratory value.
  - Lisinopril/valsartan is at mid-range (STEP 2) or maximum dose (STEP 3), pause lisinopril/valsartan and SZC/placebo, and give short-term rescue therapy as per SoC at the investigator's discretion (24 to 48 hours rescue treatment); re-start SZC/placebo after rescue and increase to 15 g QD if not already at maximum. Follow up at Visit 8 for monitoring of local S-K laboratory value.

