#### Lisinopril/Valsartan Dosing Pattern

The prescribed dose, the start, and the stop dates, as well as the timing of the dose titration of lisinopril/valsartan will be recorded and used to determine the time to the first dose change to a dose that is smaller than that taken at the point of randomisation.

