3.3.4 Multiplicity / Multiple Comparisons

Statistical testing will be performed for all primary and secondary hypotheses. In all cases, the null hypothesis will be that of no difference between the treatment arms (SZC vs placebo), with the two-sided alternative of there being a difference. Two primary hypotheses (corresponding to the evaluation of the difference in total and chronic eGFR slope, respectively) are defined in the study.

The family-wise Type I error rate will be controlled in the strong sense over the families of primary and the secondary hypotheses i.e., regardless of whether the hypotheses covered are true or false.

Two co-primary hypotheses (corresponding to the evaluation of the difference in total and chronic eGFR slope, respectively) are defined in the study. The two hypotheses will be tested in parallel (i.e., with no pre-defined order) using the whole significance level alpha.

Provided both primary hypotheses are rejected, the testing will proceed to the secondary hypotheses. A fixed sequence MTP will be applied to the family of all secondary hypotheses, with the order in the sequence following the order specified in Table 2.

In accordance with the fixed sequence MTP, significance for a hypothesis will be declared if the corresponding two-sided p-value is smaller than 0.05, provided that all other preceding hypotheses in the sequence have been rejected.

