The main strategy for handling the intercurrent events in the analysis of the primary objective will be that of treatment policy. That is, the intercurrent events that lead to a potential change in the measurements profile, but for which post-intercurrent event data are available (e.g. treatment discontinuation, introduction of eGFR altering concomitant therapy), will be ignored in the analysis, and all data obtained, both pre and post the intercurrent event, will be included as planned. In the table below, the approach for handling intercurrent events described above is referred to as “main strategy”. The exception to this rule will be the events for which it could be argued that, after experiencing these, a participant ceases to belong to the population of interest. For such an event, any data collected post event occurrence will be excluded from the main analyses. Onset of ESKD is the only type of event currently identified in this category.

In addition to the main analyses, a number of supplementary analyses of the primary and secondary endpoints, utilizing a hypothetical intercurrent event strategy, will be carried out. In this case, data from after the intercurrent events that lead to a potential change in the measurements profile will not be used in the analysis. Instead, a hypothetical scenario that the intercurrent event did not have occur will be considered. For example, for the intercurrent event of long-term potassium lowering treatment and a hypothetical strategy, it will correspond to a hypothetical situation where such treatment is not available to participants. An equivalent situation will apply to the remaining hypothetical intercurrent events.

Missing data: If not otherwise specified, no imputation of missing data will be performed. Rather, missing data will be handled indirectly through e.g., application of models for longitudinal data, such as regressions with random effects, and survival analysis approaches. The same applies for missing covariate data used in the sub-group analyses: no imputation will be performed.

One exception to this rule will be the eGFR measurements obtained as re-tests, if, due to operational reasons such as unavailability of kits, the planned eGFR samples could not be taken at a scheduled visit (see Section 4.2.1). Such measurements may be used in the eGFR-based analyses.

Covariates: For each of the model-based analyses detailed below, the following variables are included as covariates in the model:

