- Treatment (SZC vs Placebo).
- Geographic region.
- Hyperkalaemia at the beginning of the initiation phase (yes/no), as indicated by the strata applied at randomisation.
- Use of SGLT2i/Finerenone at randomisation (yes/no), as indicated by the concomitant-medications collection.
- Age.

Further covariates may be added as appropriate, and these will be specified in the descriptions below.

Table 2: Overview of the main and the supplementary analyses

|

| Statistical category | Endpoint | Intercurrent event strategy | Population level summary | Details in section |
|--|---|--|--|--------------------|
| Primary | | | | |
| Primary objective #1: To determine if treatment with S2C, as adjunct to ACEi/ARB therapy (lisinopril or valsartan), is superior to placebo in slowing CKD progression, assessed as the reduction in participant's expected eGFR decline over time | | | | |
| Main | Total slope: eGFR measurements starting at randomisation (up to visit 17/week 69) | Main strategy | Difference in mean total eGFR slopes | 4.2.1.1 |
| | Chronic slope: eGFR measurements, starting at 12 weeks after randomisation (up to visit 17/week 69) | Main strategy | Difference in mean chronic eGFR slopes | 4.2.1.1 |
| Supplementary | Total slope: eGFR measurements starting at randomisation (up to visit 17/week 69) | Hypothetical strategy wrt initiation of long-term potassium lowering treatment and initiation of potentially eGFR altering treatment | Difference in mean total eGFR slopes | 4.2.1.2 |
| | Chronic slope: eGFR measurements, starting at 12 weeks after randomisation (up to visit 17/week 69) | Hypothetical strategy wrt initiation of long-term potassium lowering treatment and initiation of potentially eGFR altering treatment | Difference in mean chronic eGFR slopes | 4.2.1.2 |

| Statistical category | Endpoint | Intercurrent event strategy | Population level summary | Details in section |
|----------------------|----------|-----------------------------|--------------------------|--------------------|
| Secondary | | | | |
| | | | | |

Secondary objective #1: To determine if treatment with SZC, as adjunct to ACEi/ARB therapy (lisinopril or valsartan), is superior to placebo in reducing the incidence of the composite of kidney failure outcomes comprising: sustained $\geq 40\%$ decline in eGFR, onset of ESKD, and death from kidney failure

| Statistical category | Endpoint | Intercurrent event strategy | Population level summary | Details in section |

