4.2.3 Analysis of Secondary objective #2

Secondary objective #2: To determine if treatment with SZC, as adjunct to ACEi/ARB therapy (lisinopril or valsartan), is superior to placebo in reducing the incidence of lisinopril/valsartan dose decrease, in participants on lisinopril/valsartan at randomisation.

Patients not on RAASi at randomization will be excluded from this analysis.

Time to dose reduction used in the model will be derived as the difference between the date of the first instance of RAASi dose decrease post-randomization and the randomization date, plus one day.

The analysis of this objective will be performed by means of a Cox regression, as described in Section 4.2.2.1.

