4.2.6.1 Main analysis

The secondary objective of evaluating the maintenance of normokalaemia will be evaluated by means of a GEE model that uses a logit link function and unstructured working correlation structure. This model will have the dichotomous classification in normokalaemic (S-K, as evaluated by c-lab, between 3.5 and 5 mmol/L) and non-normokalaemic (S-K < 3.5 or S-K > 5 mmol/L) at each visit as response. Similarly to the analysis of Secondary objective #4, the model will have visit and baseline potassium as covariates, as well as the ones specified earlier. The null hypothesis of no difference between the treatment arms will be tested by considering the estimate of the odds ratio for the treatment effect in this model. As for other analyses, the estimates of the treatment effect (i.e., odds ratios) alongside the corresponding 95% CI and p-values, will also be provided.

Again, due to the early close-down of the study and the ensuing unavailability of late potassium measurements, only measurements taken up to and including visit 17 (week 69) will be included in the GEE model; however, all available data, including the (quite few) late potassium measurements beyond visit 17 (week 69), will be summarised descriptively and listed.

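### The Cox model for time to first lisinopril/valsartan dose decrease leaves out serum potassium at randomisation, which is collected and plausibly prognostic: a modest loss of efficiency, not a validity error

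*SAP*

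**What the plan says.** SAP 4.2 sets a default: "For each of the model-based analyses detailed below, the following variables are included as covariates in the model". The list is treatment, geographic region, hyperkalaemia stratum, SGLT2 inhibitor/finerenone use and age. Its only potassium item is "Hyperkalaemia at the beginning of the initiation phase (yes/no), as indicated by the strata applied at randomisation". Any further covariate has to be named in the description of the individual analysis.

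For the dose-decrease endpoint, SAP 4.2.3 names none: "The analysis of this objective will be performed by means of a Cox regression, as described in Section 4.2.2.1". SAP 4.2.2.1, to which it refers, names none either.

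Other analyses do add a baseline value. The UACR model (SAP 4.2.4.1) adds baseline UACR, and the bicarbonate model (4.2.5.1) adds baseline bicarbonate. For normokalaemia (4.2.6.1), "the model will have visit and baseline potassium as covariates, as well as the ones specified earlier".

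Protocol 8.1.2 defines the event as "the first dose change to a dose that is smaller than that taken at the point of randomisation". After randomisation, Protocol 6.6.4 links that event to S-K. At Visit 7, with S-K above 5.0 and up to 5.5 mmol/L and SZC/placebo below its maximum, the instruction is "increase SZC/placebo to 15 g QD AND reduce lisinopril/valsartan one step".

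**The concern.** In a Cox model, omitting a covariate that predicts the event pulls the estimated hazard ratio towards 1 and lowers power, even under randomisation. S-K at randomisation is a reasonable candidate for three reasons.

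- **It is available.** A local S-K confirming normokalaemia is a condition for entering the maintenance phase (Protocol 4.1.3), and central chemistry is scheduled at Visit 6b (Protocol Table 2).
- **The protocol grades risk inside the normal range.** Inclusion criterion 5(b)(ii) treats S-K of 4.7 to 5.0 mmol/L on limited RAASi therapy as high risk. Protocol 6.6.1 names borderline high S-K as a risk factor for hyperkalaemia. The run-in titration in Protocol 6.6.3 splits at 4.7 mmol/L.
- **The stratum is coarser and older.** It is a yes/no status from before the initiation phase and about 3 months of SZC run-in. It cannot separate 3.8 from 4.9 mmol/L on the day of randomisation.

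At stake is the power and precision of the second test in the fixed secondary sequence. If that test is reached and missed, UACR, bicarbonate and normokalaemia lose formal testing.

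**Working it through.** **The plan's own power figures.** The only ones are for the co-primary slopes (Protocol 9.2). Inputs: slope difference 0.75, random-slope SD 2.6, residual SD 7.7, the 12 listed visit weeks, and 1220 participants (610 per arm).

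- SD of an estimated individual slope = √(2.6² + 7.7²/Sxx), with time in years.
- Total slope: Sxx = 6.709, SD = √(6.76 + 59.29/6.709) = 3.949. SE of the difference = 3.949 × √(2/610) = 0.2261. Power = Φ(0.75/0.2261 − 1.96) = 91.3% (stated 91%).
- Chronic slope (week 12 on): Sxx = 4.858, SD = 4.355, SE = 0.2494. Power = Φ(0.75/0.2494 − 1.96) = 85.3% (stated about 85%).
- 1220/0.9 = 1356 (stated 1360).

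All three reproduce, but none bears on the dose-decrease endpoint. Neither document gives its event rate, hazard ratio or power, so everything below rests on assumed inputs.

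**Simulation of the omission.** Fixed by the documents: a two-sided 0.05 test ("significance for a hypothesis will be declared if the corresponding two-sided p-value is smaller than 0.05"), 1:1 allocation ("Participants will be randomised in a 1:1 ratio to receive either SZC or matching placebo") and two years of follow-up. Assumed: N, hazard ratio (HR), event proportion, and τ, the SD of log-hazard carried by the omitted covariate beyond what the model already holds. The hazard multiplies by e^τ per SD of the covariate: 1.22 at τ = 0.2, 1.49 at 0.4, 1.82 at 0.6 and 2.23 at 0.8. Event times are exponential. There are 600 replicates per cell at N = 1220 and 1000 at N = 400, and simulation error on each power is about 1 to 2 points.

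Power without → with the covariate:

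| Scenario | τ = 0.2 | τ = 0.4 | τ = 0.6 | τ = 0.8 |
|---|---|---|---|---|
| N 1220, HR 0.80, 50% events | 77.7 → 78.8 | 71.7 → 76.3 | 69.8 → 77.5 | 64.5 → 80.7 |
| N 400, HR 0.70, 50% events | 68.0 → 69.3 | 68.9 → 72.3 | 58.6 → 69.2 | 57.5 → 70.7 |
| N 400, HR 0.70, 25% events | 41.3 → 43.1 | 37.8 → 39.6 | 38.3 → 42.1 | 35.1 → 40.9 |
| N 400, HR 0.70, 70% events | 82.8 → 83.9 | 81.3 → 85.8 | 70.6 → 83.7 | 66.1 → 82.2 |
| Range of gain (points) | 1.1 to 1.8 | 1.8 to 4.6 | 3.8 to 13.1 | 5.8 to 16.2 |

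**Checks.**

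- Schoenfeld's formula, Φ(√d/2 × |ln HR| − 1.96), with d = 200 and HR 0.70 gives Φ(7.071 × 0.3567 − 1.96) = 71.3%. The adjusted model in that scenario gives 69.2% to 72.3%.
- With HR = 1, N = 400, 50% events, τ = 0.6 and 3000 replicates, rejection is 4.8% without the covariate and 4.6% with it.
- At true HR 0.70, 50% events and τ = 0.8, the model without the covariate averages 0.74 and the model with it 0.70.
- With staggered follow-up (N = 400, HR 0.70, 2000 replicates), the gain at SD 0.2 to 0.4 is 0.4 to 1.6 points at a 30% event rate and 1.7 to 4.0 points at 50%.

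**The case against.** The case for leaving the model alone has real force.

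- **Choice of comparator.** UACR, bicarbonate and S-K are laboratory outcomes with a baseline of their own. A time to first dose decrease has none. The closer comparator is secondary #1, whose Cox model also uses only the common list. This stands: the SAP treats its two Cox models alike, so the omission is a missed opportunity rather than a clear inconsistency.
- **Does S-K at randomisation drive the decrease?** A reader might infer that it does. The documents do not support that. The titration rules act on S-K measured after randomisation, and doses may also fall for hypotension, a creatinine rise, low eGFR or an adverse event (Protocol 4.3.2, 6.6.5 and 7.1.2). S-K at randomisation is a plausible predictor, not a trigger.
- **RAASi dose at randomisation.** A reader might call its omission equally costly. Its support is only indirect. The dose step decides between a step down and a pause or discontinuation, but the documents give no direction of prognostic effect, and SAP 4.2.3 does not say whether a pause counts as a decrease.
- **Restricted range.** Everyone randomised must have S-K of 3.5 to 5.0 mmol/L, measured on SZC. Pre-SZC hyperkalaemia, already in the model, may predict rebound as well or better. This stands as a reason to expect the lower part of the range, but the documents do not show that the stratum makes S-K at randomisation redundant.
- **Blocking later tests.** A reader might conclude that this choice costs the trial three further secondary tests. Under SAP 3.3.4, objective #2 is tested only if both co-primaries and secondary #1 are rejected, and the study was terminated early. The sequence may well stop before reaching it.

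**Conclusion.** The point holds as a modest, optional efficiency gain. The omission is plain from SAP 4.2, 4.2.2.1 and 4.2.3, and the direction of its effect is not in doubt. Its size cannot be derived from the documents. Under the assumed scenarios the gain is about 1 to 5 points at a residual log-hazard SD of 0.2 to 0.4, and about 4 to 16 points at 0.6 to 0.8. The lower band is the safer expectation, given the truncated potassium range and what the stratum already carries. The larger gains require the hazard to rise by about 80% or more per SD of S-K among people who are all normokalaemic.

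It would be wrong to read this as a biased or invalid test. The planned model controls type I error. Pulling the hazard ratio towards 1 costs sensitivity, not false positives. If the testing sequence stops earlier, what remains is mainly a more precise description of the effect.

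**What to change.** In SAP 4.2.3, before unblinding, add S-K at randomisation as a continuous covariate and keep the current model as a sensitivity analysis. Name the laboratory. The local value required for randomisation should exist for every correctly randomised participant. A missing central value at Visit 6b would drop a participant from the model, because SAP 4.2 makes no imputation by default. If the local value is used, check it against the 5-day baseline window of SAP 3.3.1.1.

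Adequate RAASi dose at randomisation (yes/no, already listed in SAP 4.1.6.1) may be added as a second option, with the weaker rationale acknowledged.

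The cost is one sentence in the SAP and no new data. The downside is that the hazard ratio becomes conditional on the added covariate, so it is not the same quantity as the current one. If unblinding has already taken place, report the adjusted model as supportive only.

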4.2.4 Analysis of Secondary objective #3

Secondary objective #3: To determine if treatment with SZC, as adjunct to ACEi/ARB therapy (lisinopril or valsartan), is superior to placebo in reducing albuminuria.

4.2.4.1 Main analysis

The evaluation of the secondary objective of assessing the UACR level will be performed by means of a linear regression model. The model will have UACR levels obtained post randomization (at visit 13, corresponding week 24 post randomization) as response and include baseline (pre-maintenance phase) UACR as an explanatory variable, in addition to the ones specified [in the beginning of Section 4.2](#). Provided will be the estimate of the treatment difference together with a 95 % CI and a p-value for a test of no treatment difference.

4.2.4.2 Supplementary analysis

The supplementary analysis will examine the UACR percent change from baseline. This will be done by means of fitting a linear regression model to the natural logarithm of fold-change from baseline in UACR at Visit 13, i.e., to $\ln(\text{UACR}[\text{visit 13}]/\text{UACR}[\text{baseline}])$, on patient level. Besides the ones specified [above](#), the model will also include the natural logarithm of baseline (pre-maintenance phase) UACR as explanatory variable.

The results will be back-transformed via application of $(e^{<<\text{value}>>} - 1) \times (100\%)$, with $<<\text{value}>>$ referring to the estimates, as well as the upper and lower CI limits, of the model fitted to the log transformed values, expressing the results as a percent change/difference.

4.2.4.3 Supportive analyses

Cross-tabulations of UACR class at baseline (<300, 300 – 1000, >1000, missing [mg/g]) against the post-baseline UACR class will also be provided.

4.2.5 Analysis of Secondary objective #4

Secondary objective #4: To determine if treatment with SZC, as adjunct to ACEi/ARB therapy (lisinopril or valsartan), is superior to placebo in increasing serum bicarbonate levels.

4.2.5.1 Main analysis

The evaluation of the secondary objective of assessing the serum bicarbonate level will be performed by means of a linear mixed model. The model will have bicarbonate levels obtained at scheduled visits post randomization as response and include the following covariates in the fixed-effects part, in addition to the ones specified [in the beginning of Section 4.2 above](#):

- Visit (factor)
- Baseline (pre-maintenance phase) bicarbonate

The model will also include a random intercept within patient. Note that the model assumes a constant treatment effect over time, this assumption evaluated in the supplementary analysis described below. The null hypothesis of no difference between the treatment arms will be tested by considering the treatment effect estimate in this model. As for other analyses, the estimates for the two treatment arms, as well as the treatment effect (i.e., difference in means between the two treatment arms) alongside the corresponding 95% CIs and p-value, will be provided.

Again, due to the early close-down of the study and the ensuing unavailability of late bicarbonate measurements, only measurements taken up to and including visit 17 (week 69) will be included in the mixed-effects model; however, all available data, including the (quite few) late bicarbonate measurements beyond visit 17 (week 69), will be summarised descriptively and listed.

